### **5.7.5. Analysis of Secondary and Other Efficacy Endpoints**

#### **5.7.5.1. Time to event endpoints**

For all time to event endpoints, the primary treatment comparison between the active treatment and the placebo (10 mg/kg mavrilimumab vs. placebo, and 6 mg/kg mavrilimumab vs. placebo) will be based on log-rank test stratified by the actual randomization strata.

The Kaplan-Meier (KM) method will be used to estimate the survival distribution function for all the time to event endpoints. The 25th, 50th (median), 75th percentiles and their two-sided 80% confidence interval (CI) will be estimated. In addition, the probability of favorable outcome (event rates, or event-free rates depending on the endpoints) at Day 4, 8, 15, 22 and 29 will be calculated, along with their standard errors using Greenwood's formula (Klein, 2003) stratified by the actual randomization strata. Corresponding Kaplan-Meier plot will be produced. In case of favorable outcomes, the plot will be based on 1-KM.

The hazard ratio for (10 mg/kg mavrilimumab vs. placebo) or (6 mg/kg mavrilimumab vs. placebo) and the corresponding Wald 80% CI will be calculated based on a Cox proportional-hazards model with treatment as covariates, stratified by the actual randomization strata.

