**The efficacy and safety results from the KPL-301-C203, Phase 2 Cohort 1 subjects**, support use of both doses of mavrilimumab in the ongoing Phase 3 study. While generally there are no apparent differences between the two mavrilimumab arms for efficacy and safety, given the small number of primary events of ventilation and/or death analyzed to date, there are some differences between the two doses in mortality (10 mg/kg is numerically efficacious) or ventilation-free survival (6 mg/kg is numerically more efficacious). Overall, both the 10 mg/kg and the 6 mg/kg appear well-tolerated with no new identified safety risks in the COVID-19 study population. In fact, serious infections (e.g., septic shock, sepsis) were substantially lower in both mavrilimumab dose arms compared to placebo, and thrombosis events were only reported in the placebo arm. There were no serious adverse events related to mavrilimumab, no dose-related adverse events and no infusion reactions.

**Important potential risks for mavrilimumab** will continue to be monitored. These include severe hypersensitivity reactions, immune complex disease, serious infections (viral, bacterial, and opportunistic infections), malignancy, vaccine interactions, pulmonary alveolar proteinosis, reproductive toxicity and granulocytic effects, including neutropenia. Of note, there is no biological rationale for several of these potential risks in the setting of a single dose administration. More importantly, none of these potential risks have been identified in the RA development program through Phase 2b with approximately 900 subject-years of exposure. See Investigator's Brochure for additional details.

This clinical study was designed and shall be implemented, executed, and reported in accordance with the ICH Tripartite Guidelines for Good Clinical Practice, with applicable local regulations, US Code of Federal Regulations (CFR) 21, and with the ethical principles laid down in the Declaration of Helsinki.

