#### 13.2.4.2. Secondary and Other Efficacy Endpoints

Ventilation-free survival, overall survival, [REDACTED] time to clinical improvement, and all other time to event endpoints will be analyzed using log-rank test stratified by randomization strata. These time to event endpoints will be summarized with the 25th, 50th (median), and 75th percentiles using the Kaplan-Meier method. The 80% (for Phase 2) and 95% (for Phase 2 and 3) CIs for the percentiles will be calculated using a log-log transformation. The percentage of subjects with events and its 80% (for Phase 2) and 95% (for Phase 2 and 3) CI will

be calculated at Day 4, 8, 15, 22 and Day 29 since randomization as appropriate, using Greenwood's formula with a log-log transformation.

The hazard ratio for mavrilimumab vs. placebo and the corresponding Wald 80% (for Phase 2) and 95% (for Phase 2 and 3) CI will be calculated based on a Cox proportional-hazards model with treatment as covariate, stratified by randomization strata.

All binary endpoints in both cohorts for Phase 2 will be primarily analyzed using the Fisher's exact test. The CMH test adjusting for randomization strata (authorized standard of care antiviral therapy for COVID-19 [eg, remdesivir], age, and ARDS status) will be used as supportive analysis for Cohort 1 (non-ventilated subjects).

For the Phase 3 part of the study, the CMH test adjusted by randomization strata will be used to test all binary secondary and other efficacy endpoint for both cohorts.

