### 1.4. Sample Size Justification

Sample sizes were calculated separately for each cohort and phase of the study based on their primary endpoint and other assumptions. Key elements for Phase 2 sample size are summarized below with type I error of 0.20 and power of 80%.

Cohort	KPL-301	Placebo	Sample Size	Primary Endpoint
1	95%	75%	120	D29 Proportion of subjects alive and free of ventilation
2	40%	80%	51	D29 Mortality rate

Approximately 171 subjects will be randomized to the Phase 2 part of this study.

Sample size estimation for Cohort 1 (non-ventilated subjects) in Phase 2 is based on the primary efficacy endpoint proportion of subjects alive and free of mechanical ventilation at Day 29, using a Fisher’s exact test.

Approximately 120 subjects will be randomized with a 1:1:1 allocation ratio. Assuming the proportions of subjects alive and free of ventilation at Day 29 are 95% and 75% for the active treatment arm and placebo arm, respectively, 40 subjects per arm will achieve a minimum 80% power for a pairwise comparison versus control when the two-sided alpha value is 0.20.

Sample size for Cohort 2 (ventilated subjects) in Phase 2 is based on the primary efficacy endpoint mortality rate at Day 29, using a Fisher's exact test. Approximately 51 subjects will be randomized with a 1:1:1 allocation ratio. Assuming the mortality rates at Day 29 are 40% and 80% for the active treatment arm and placebo arm, respectively, 17 subjects per arm will achieve 80% power for a pairwise comparison versus control when the two-sided alpha value is 0.20.

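### In Phase 2 Cohort 1, a dose arm has about a 13% chance of no ventilation-or-death event at the planning rates, and the planned Cox hazard ratio and Wald interval then cannot be estimated

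*Combined protocol and SAP*

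**What the plan says.** Phase 2 SAP section 5.7.5.1 compares "10 mg/kg mavrilimumab vs. placebo, and 6 mg/kg mavrilimumab vs. placebo", with the test "based on log-rank test stratified by the actual randomization strata". The hazard ratio comes with it as the effect estimate, and "the corresponding Wald 80% CI will be calculated based on a Cox proportional-hazards model with treatment as covariates". Protocol section 13.2.4.2 agrees on the type of interval: "the corresponding Wald 80% (for Phase 2) and 95% (for Phase 2 and 3) CI".

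Phase 2 SAP section 5.7.3 includes time to ventilation or death by Day 29 (Cohort 1) and overall survival by Day 29 or Day 90 among the time-to-event endpoints. Neither is listed as primary or secondary in sections 2.1 and 2.2 of that SAP.

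The Cohort 1 planning rates in section 1.4 are "95% and 75% for the active treatment arm and placebo arm, respectively", and "40 subjects per arm will achieve a minimum 80% power for a pairwise comparison versus control when the two-sided alpha value is 0.20". Protocol section 13.3.1 adds that this allows for 15% dropout.

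Two sets of rules deal with sparse strata. Phase 2 SAP section 4.1 pools a stratum that has fewer than 5 subjects, no event in either arm, or identical responses throughout. Protocol section 13.2.2 pools strata with 5 or fewer events for the log-rank test. Both can end in an unstratified analysis. Neither says what to report when a whole dose arm has no event.

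**The concern.** A Wald interval relies on a finite estimate and a roughly quadratic log-likelihood around it. The plan's own rates imply about 2 events in a dose arm, too few to rely on either. Each dose is compared with placebo separately, so the other dose's events cannot help. The failure is also most likely when the drug works best.

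If it happened, the analyst would have to choose another method after unblinding. At stake is one effect measure on two lower-tier Phase 2 endpoints; the primary result is not touched.

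**Working it through.** **Inputs.** 40 per arm; 95% active and 75% placebo alive and ventilation-free at Day 29 (Phase 2 SAP 1.4); 15% dropout (protocol 13.3.1), so 40 × 0.85 = 34 evaluable. The Day 29 failure rates, 5% and 25%, are taken as event rates, which is an assumption.

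**The plan's own figure.** Exact enumeration of Fisher's test at two-sided 0.20, 95% vs 75%, gives power of 80.6% at 34 per arm and 85.7% at 40. The stated minimum of 80% is reproduced, so these are the rates behind the design.

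**Why no event means no estimate.** Let b be the log hazard ratio, and let an event occur when n1 active and n0 placebo subjects are at risk. If every event is on placebo, each adds −log(n0 + n1·e^b) to the log partial likelihood. This rises steadily as b falls, so the maximum lies at b = −∞. The hazard ratio goes to 0 and its Wald standard error diverges. Pooling or dropping strata changes n0 and n1 but leaves the arm empty.

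**How likely.** With event rate q and n per arm, the expected count is nq, P0 = (1 − q)^n, and the chance for at least one of two dose arms is 1 − (1 − P0)².

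| Event rate, n | Expected events | P0, one dose | At least one of two |
|---|---|---|---|
| 5%, 40 | 2.0 | 12.9% | 24.0% |
| 5%, 34 | 1.7 | 17.5% | 31.9% |
| 12.5%, 40 | 5.0 | 0.5% | 1.0% |

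Placebo expects 40 × 0.25 = 10 events. Using 34 treats dropouts as contributing nothing, whereas a Cox model would use their time before censoring, so 12.9% and 17.5% bracket the planning case. The 12.5% row is 100% − 87.5%, the active rate in protocol 13.3.2, which was adjusted on Phase 2 results.

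**Overall survival.** Deaths by Day 29 are a subset of ventilation-or-death events by Day 29, so an empty arm is at least as likely. No Cohort 1 death rate is given. For assumed rates of 4%, 2.5%, 2% and 1% with n = 40, P0 is 19.5%, 36.3%, 44.6% and 66.9%.

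**Coverage when the interval exists.** In 4,000 simulated trials per setting (exponential times over 28 days, 5% vs 25%, 40 per arm):

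- Unstratified: no finite estimate in 13.2%; the nominal 80% Wald interval covered 87.0% of the rest.
- Eight strata: 13.5% and 87.8%.
- 34 per arm, unstratified: 17.1% and 86.8%.

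**Alternative interval.** In simulations of the same design, a Firth-penalized Cox model with a profile-likelihood interval covered about 80% to 83% at the planning rates and 79% to 81% at the later rates. Its upper limit was finite in essentially every trial.

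**Where it does not apply.** Cohort 2 expects 17 × 0.40 = 6.8 deaths per active arm, and 0.60^17 = 0.02%. The secondary time-to-event endpoints count improvement or return to room air, which are favourable and frequent. Phase 3 at its planning rate expects 200 × 0.125 = 25 events per active arm.

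**The case against.** The strongest reply is that little is lost. The comparison is the stratified log-rank test, which still works with an empty arm. Kaplan-Meier rates are reported at set days, and the Day 29 outcomes are tested as proportions by Fisher's exact test, with an exact interval for the primary one. The two endpoints are neither primary nor secondary in Phase 2. All of this stands and keeps the point minor.

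A second reply is that the later rate makes the problem rare: about 0.5% at 12.5% events, where simulated Wald coverage was 80% to 81%. That also stands, but the figure was set after the Phase 2 results, and the Phase 2 SAP has to work at the rates it was designed on.

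A third is that an eight-stratum fit is not the planned analysis, because the pooling rules would collapse it at about 12 events (2 + 10). This is correct, but the unstratified results are nearly the same.

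Two stronger readings are tempting, and neither is supported:

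- **Under-coverage.** A reader might score trials without an interval as misses and infer about 76% overall coverage (75.6% unstratified). But an interval from 0 to infinity contains the true value. Counted that way, coverage is 13.2% + 75.6% = 88.8%. The fault is non-estimability and conservatism.
- **Decision impact.** A reader might infer that these hazard ratios shaped the dose rationale or the Phase 3 endpoint list. The protocol's dose rationale describes only numerical differences between the doses, "given the small number of primary events of ventilation and/or death analyzed to date", and cites no hazard ratio. The Phase 3 sample size uses proportions. The summary of changes says endpoints were revised on Phase 2 results without naming a hazard ratio.

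**Conclusion.** The point holds for Phase 2 Cohort 1 time to ventilation or death and overall survival, as a low-priority improvement. At the planning rates, the hazard ratio and Wald interval for ventilation or death cannot be estimated with probability 12.9% per dose and 24% for at least one dose (17.5% and 32% at 34 per arm). When the interval exists, it over-covers, at about 87% against 80%. For overall survival by Day 29 the chance is higher by an amount the documents do not fix.

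These figures rest on taking the Day 29 failure rate as the event rate. Subjects ventilated and later extubated could add events; counting early terminations as non-responders (Phase 2 SAP 5.7.2) could mean fewer true events. At an 8% event rate the per-arm chance is 0.92^40 = 3.6%. The documents do not report arm-level event counts, so they do not show whether an empty arm occurred.

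**What to change.** In Phase 2 SAP section 5.7.5.1, for Cohort 1 time to ventilation or death and overall survival, replace the Wald interval with a profile-likelihood 80% interval from a Firth-penalized stratified Cox model, and report that model's hazard ratio. In SAS this is the FIRTH and RISKLIMITS=PL options of PROC PHREG. Keep the stratified log-rank test as the comparison, and align protocol section 13.2.4.2. If Phase 2 has already been analysed, leave the prespecified result in place and add this as a labelled supplementary estimate.

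The cost is one sentence of SAP text and two program options; sample size, data collection and conduct do not change. The downside is slight shrinkage of the hazard ratio. A smaller alternative is one sentence stating what is reported when an arm has no event. That would close the main gap but leave the over-coverage.

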#### **5.7.5.2. Binary (rate or proportion) endpoints**

The primary treatment comparison for all binary endpoints will be based on the Fisher's exact test. Number of subjects and percentages will be summarized by treatment. The 80% confidence interval (CI) of the difference in the proportion (KPL-301 – placebo) based on normal approximation will be provided.

The event rates (or event-free) from the corresponding time to event analysis can serve as supportive analyses. For example, proportion of subjects with K-point clinical improvement can be estimated from time to K-point clinical improvement; mortality rate can be estimated from the overall survival. No formal testing will be conducted.

#### **5.7.5.3. Endpoints to be summarized descriptively**

Descriptive statistics (n, mean, standard deviation, median, minimum and maximum) will be used to summarize the following endpoints. No imputation will be done unless otherwise specified.

- [REDACTED]
- [REDACTED]

- [REDACTED]
- [REDACTED]  
[REDACTED]
  - [REDACTED]
  - [REDACTED]
- [REDACTED]
- [REDACTED]
- [REDACTED]
  - [REDACTED]
  - [REDACTED]
  - [REDACTED]
  - [REDACTED]

#### 5.7.6. Subgroup analysis

Subgroup analyses will be conducted for each of the randomization stratum for the primary efficacy endpoint. The same statistical methods and conventions used for the primary efficacy endpoint will apply.

### 5.8. Safety Analysis

The safety endpoints will be tabulated by treatment based on the Safety Analysis Set. All safety data including those collected during the safety follow-up will be listed by subject.

#### 5.8.1. Adverse Events

An adverse event (AE) is any untoward medical occurrence in a subject or clinical investigation subject administered a pharmaceutical product. An AE does not necessarily have a causal relationship with this treatment. An AE will be defined as treatment-related if its relationship to the study drug is reported as Possibly Related or Definitely Related by Investigator.

An AE is considered treatment-emergent adverse event (TEAE) if the AE begins on/after and within 90 days of the study drug administration. If the date of AE onset is missing or coincides with the date of the study drug administration and AE time is not captured, AE will be considered treatment-emergent.

All AEs will be coded using MedDRA version 23.0. A subject experiencing multiple AEs under the same preferred term (PT) or same system organ class (SOC) will be counted only once for that PT or SOC by maximum severity. If a subject experience the same AE more than once with more than one causal relationship to study drug, the strongest causal relationship to study drug will be given precedence. Any missing severity, causality, or outcome will not be imputed and classified as 'Missing'. Detailed imputation rules for missing AE dates are in Section [8.1.1](#).

An adverse event of special interest (AESI) is one of scientific and medical interest specific to understanding of the Investigational Product and requires close monitoring and rapid communication by the investigator to the sponsor. An AESI may be serious or non-serious.

The number of subjects with at least one TEAE will be tabulated. The following tables summarize incidences of various aspects of TEAEs, treatment-emergent serious AEs (TESAEs), and treatment-emergent AESIs (TEAESIs):

- Overview of TEAEs (summary of all the subsequent items)
- TEAEs by SOC and PT
- TEAEs by PT
- TEAEs by maximum severity (mild, moderate, or severe)
- Drug related TEAEs (related or not related) by SOC and PT
- TESAEs by SOC and PT
- Drug related TESAEs by SOC and PT
- TESAEs by PT
- TEAESIs by SOC and PT
- TEAEs leading to dose interruption by SOC and PT
- TEAEs leading to death by SOC and PT

All information pertaining to adverse events will be listed by subject, detailing verbatim term given by the investigator, preferred term, system organ class, start date, stop date, severity, outcome, action taken and drug relatedness.

Separate listings will be created for Serious TEAEs, and TEAESI, and death.

Additionally, non-serious TEAEs by SOC and PT will be tabulated.

### **5.8.2. Clinical Laboratory Parameters**

The following laboratory analyses are performed at the Study Site/Clinic laboratories and recorded on the eCRF:

- Screening for tuberculosis
- Pregnancy
- SARS-CoV-2 test with RT-PCR
- Hematology: complete blood count + differential
- Chemistry: electrolytes, blood urea nitrogen, glucose, and CR
- Liver profile: AST, ALT, Alb, AlkP, Tbili, Dbili
- Lipid panel: Cholesterol, total; high-density lipoprotein (HDL) cholesterol; low-density lipoprotein (LDL) cholesterol (calculation); triglycerides; very low-density lipoprotein (VLDL) cholesterol (calculation)
- Urinalysis
- [REDACTED]

The following tests are performed by the central lab:

- [REDACTED]
- [REDACTED]
- [REDACTED]

Continuous laboratory data ([REDACTED], hematology, coagulation, chemistry, liver profile, lipid panel, urinalysis) will be examined for trends using descriptive statistics of actual values and changes from baseline over time by treatment for the safety analysis set.

Urinalysis will be summarized categorically.

Shift tables will be produced for hematology and chemistry.

All laboratory results will be presented in by-subject listings.

### 5.8.3. Vital Signs

Vital signs include temperature, respiratory rate, systolic blood pressure/ diastolic blood pressure, and heart rate. Body weight and height will be reported in Body Measurements eCRF.

Actual values of vital signs (including weight) and changes from baseline will be summarized using descriptive statistics by visit.

All vital signs data will be listed.

### 5.8.4. Electrocardiogram (ECG)

All ECG data will be listed.

### 5.8.5. Physical Examination

All physical examination data will be listed.

### 5.8.6. Chest Imaging

Chest imaging data will be listed.

## 6. CHANGES TO PLANNED ANALYSES FROM THE PROTOCOL

- The SAP is for Phase 2 only and a separate SAP will be developed for the Phase 3 part of the study
- The following other efficacy endpoints are out of scope for this SAP, and will be reported separately

- [REDACTED]
- [REDACTED]

○ [REDACTED]

## 8. APPENDICES

### 8.1. Handling of Missing Safety Data

No imputation will be made for completely missing date unless otherwise specified. General imputation rules mentioned below apply to partially missing or impossible dates:

- If the stop date is not missing, and the imputed start date is after the stop date, the start date will be imputed by the stop date
- If the start date is not missing, and the imputed stop date is before the start date, then the imputed stop date will be equal to the start date
- Any imputed dates need to be logical. For example, last dose date should not be later than death date.

When imputation rules in subsequent sections contradicts the general rule, always follow the general rule.

#### 8.1.1. Adverse Event Date Imputation

Follow the general rule specified in Section 8.1.

##### **Incomplete Start Date:**

*Missing day, month, and year*

No imputation will be made; the corresponding AE will be included.

*Missing day and month*

- If the year is the same as the year of the first dose date, then impute day and month as the day and month of the first dose
- If the year is prior to the year of the first dose date, then impute day and month as 31 Dec
- If the year is after the year of the first dose date, then impute day and month as 01 Jan.

*Missing day only*

- If the month and year are the same as those of the first dose date, then impute day as the day of the first dose date

- If either the year of partial date is before the year of the first dose date, or the years are the same, but the month of partial date is before the month of the first dose date then impute day as last day of the month
- If either the year of partial date is after the year of the first dose date, or the years are the same, but the month of partial date is after the month of the first dose date, then impute day as first day of the month.

**Incomplete Stop Date:**

*Missing day, month, and year*

- No imputation will be made.

*Missing day and month*

- If the year is the same as the year of the last dose date, then impute day and month as the day and month of the last dose date
- If the year is prior to the year of the last dose date, then impute day and month as 31 Dec
- If the year is after the year of last dose date, then impute day and month as 01 Jan.

*Missing day only*

- If the month and year are the same as those of the last dose date, then impute day as the day of the last dose date
- If either the year of partial date is not the same as the year of the last dose date, or the years are the same, but the month of partial date is not the same as the month of the last dose date, then impute day as last day of the month.

**8.1.2. Concomitant Medication Date Imputation**

Follow the general rules specified in Section [8.1](#) and Section [8.1.1](#).

Signature Page for RIM-CLIN-000916 v1.0

Approval	
Approval	
Approval	
Approval	

Signature Page for RIM-CLIN-000916 v1.0

Approval	
----------	--

Approval	
----------	--

Approval	
----------	--

Approval	
----------	--

Signature Page for RIM-CLIN-000916 v1.0
